## 2. INTRODUCTION

ETEC remains a major cause of childhood diarrhea in low-middle income (i.e., developing) countries and is endemic to areas with poor infrastructure for sanitation and without access to clean water. The use of dmLT is proposed as an oral, sublingual (SL), or intradermal (ID) traveler's diarrhea vaccine for persons from industrialized (i.e., developed) countries that visit high-risk developing (non-industrialized) countries. It is envisioned that dmLT may also be used as a component of candidate ETEC vaccines under development for use in infants and young children living in ETEC endemic areas. The National Institute of Allergy and Infectious Disease (NIAID) sponsored a Phase 1 dose-escalation study of healthy adult participants who received a single oral dose of dmLT (DMID Protocol 09-0066). No participants experienced diarrhea in any dosage group and the vaccine was well tolerated. Although the immune responses were limited in those receiving 5 µg or 25 µg of dmLT, the immune response was greater in those receiving 50 µg or 100 µg of dmLT, with a possible plateauing of immune responses at 50 µg. A Phase 1 study of an inactivated oral multivalent ETEC vaccine (ETVAX, expressing CFA/I, CS3, CS5, CS6, and LTB) with dmLT as an adjuvant was conducted in 129 healthy Swedish adults. The vaccine with dmLT was safe and well tolerated; dmLT appeared to further enhance mucosal immune responses to CF antigens which were present in low amounts in the vaccine. A Phase 1/2 study (VAC 014/OEV-122) of oral administration of an inactivated ETEC vaccine (ETVAX) with and without dmLT and a Phase 2 study (NCT02531802) of the oral ETEC vaccine (ETVAX) administered with dmLT among healthy adults in Bangladesh are ongoing at the International Centre for Diarrhoeal Disease Research, Bangladesh (icddr,b). A Phase 1/2b study of a live, attenuated oral ETEC vaccine (ACE527) adjuvanted with dmLT was conducted in the United States (VAC 006). The trial results have not yet been published, but the data have been presented at scientific conferences. Immunization with ACE527 administered with dmLT was safe and immunogenic and protecting against diarrhea upon challenge. NIAID sponsored a Phase 1 dose-escalation study in healthy adult participants who received three sequential SL or Oral doses of dmLT (DMID Protocol 12-0023). Delivery of dmLT to Cohorts 1-4 were completed and no safety concerns were identified with up to the 3 doses of 50 µg dmLT delivered orally. The study is completed; there have been no noted safety concerns. There are no other human trials, to our knowledge, that have been completed using SL route of administration of dmLT as a vaccine or adjuvant. NIAID is currently sponsoring a Phase 1 dose-escalation trial with dmLT administered in three sequential doses via the ID route (DMID Protocol 13-0013), the first in human trial with dmLT administered via the ID route. The trial has progressed through doses up to 2.0 µg without safety concerns. The aforementioned DMID-sponsored studies on dmLT have been or are being conducted in the United States (an industrialized country) and there are unanswered questions regarding the immune responses through different routes of administration in a non-industrialized country. This study was designed to assess the safety and immune responses of a range of doses of dmLT when administered by the oral, SL, or ID route, in participants residing in an endemic country for ETEC disease. Compared to oral immunization, SL or ID immunization may increase dose-sparing, which would help reduce the cost of the final vaccine product, and potentially eliminate the need for buffering to neutralize gastric acid, therefore providing greater protein antigen stability. Both the SL and ID routes may also help bypass gut enteropathy, a major barrier to oral vaccination. The proposed indication for dmLT is to protect against ETEC diarrhea associated with infection by strains expressing the *E. coli* heat-labile enterotoxin alone or in combination with the heat-stable toxin as a component of an oral, sublingual, or intradermal diarrhea vaccine for those residing in high risk endemic regions as well as international travelers to these high-risk regions.

---

## **2.1. Purpose of the Analyses**

These analyses assess the safety, reactogenicity, and immunogenicity of a range of doses of dmLT administered via the oral, sublingual, or intradermal route and will be included in the clinical study report.

### 3. STUDY OBJECTIVES AND ENDPOINTS

#### 3.1. Study Objectives

##### Primary

- To assess the reactogenicity, safety and tolerability of dmLT when administered in three sequential doses, over a range of dosages by oral, sublingual, or intradermal routes

##### Secondary

- To assess the long-term safety, from first vaccination through 6 months following the last dose of vaccine
- To evaluate the serum anti-dmLT Immunoglobulin IgG and IgA response
- To evaluate the IgG and IgA anti-dmLT Antibody Secreting Cell (ASC) response
- To evaluate the IgG and IgA anti-dmLT Antibodies in Lymphocyte Supernatant (ALS) response
- To evaluate the total fecal IgA and fecal anti-dmLT IgA response
- To evaluate the total salivary IgA and the saliva-derived anti-dmLT IgA response

##### Exploratory

- To measure the mucosal homing of IgA anti-dmLT ASC
- To measure the serum toxin neutralizing antibody response
- To measure the dmLT-specific IgG and IgA memory B cell response
- To determine the dmLT-specific effector and memory T cell responses

#### 3.2. Endpoints

##### 3.2.1. Primary Outcome Measures

The **Primary Safety Endpoints** to be used to evaluate reactogenicity, safety and tolerability are as follows:

- The occurrence of solicited local site and systemic reactogenicity events from vaccination through 7 days after each dose of vaccine is administered
- The occurrence of study withdrawals throughout the study
- The occurrence of discontinuation of study vaccination during the study
- The occurrence of unsolicited vaccine-related adverse events (AE), including laboratory AE, from first vaccination through 28 days after the last dose of vaccine is administered

##### 3.2.2. Secondary Outcome Measures

The **Secondary Safety Endpoints** to be used to evaluate the safety of this study are:

- The occurrence of vaccine-related serious adverse events (SAE) from the first vaccination through 6 months after the last dose of vaccine was administered
-

The **Secondary Immunogenicity Endpoints** to be used to evaluate the immune response to vaccination consist of the following:

- At any time after vaccination, the proportion of participants with a  $\geq 4$ -fold rise in dmLT-specific serum IgG and IgA titers over baseline measured by Enzyme-Linked Immunosorbent Assay (ELISA)
- At any time after vaccination the proportion of participants with  $\geq 8$  dmLT-specific IgA or IgG ASC /  $10^6$  peripheral blood mononuclear cells (PBMC) as measured by Enzyme-Linked ImmunoSpot Assay (ELISpot)
- At any time after vaccination, the proportion of participants with  $\geq 2$ -fold rise in ALS anti-dmLT-specific IgG and IgA titers over baseline measured by ELISA
- At any time after vaccination, the proportion of participants with a  $\geq 4$ -fold rise over baseline in dmLT-specific fecal IgA titers measured by ELISA
- At any time after vaccination, the proportion of participants with a  $\geq 4$ -fold rise over baseline in dmLT-specific salivary IgA titers measured by ELISA

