3.2.2 Secondary Outcome Measures

The **Secondary Safety Endpoints** to be used to evaluate the safety of this study are:

- The occurrence of vaccine-related serious adverse events (SAE) from the first vaccination through 6 months after the last dose of vaccine is administered

The **Secondary Immunogenicity Endpoints** to be used to evaluate the immune response to vaccination will consist of the following:

- At any time after vaccination, the proportion of participants with a ≥ 4 -fold rise in dmLT-specific serum IgG and IgA titers over baseline measured by ELISA
- At any time after vaccination the proportion of participants with > 8 dmLT-specific IgA or IgG ASC / 10^6 PBMC as measured by ELISpot
- At any time after vaccination, the proportion of participants with ≥ 2 -fold rise in ALS anti-dmLT-specific IgG and IgA titers over baseline measured by ELISA
- At any time after vaccination, the proportion of participants with a ≥ 4 -fold rise over baseline in dmLT-specific fecal IgA titers measured by ELISA
- At any time after vaccination, the proportion of participants with a ≥ 4 -fold rise over baseline in dmLT-specific salivary IgA titers measured by ELISA

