- A life-threatening adverse event, defined as an adverse event the occurrence of which, in the view of either the site principal investigator or sponsor, places the participant at immediate risk of death. It does not include an adverse event that, had it occurred in a more severe form, might have caused death.
- Inpatient hospitalization (defined by local practice as the study participant being present in the hospital greater than 24 hours) or prolongation of existing hospitalization,
- A persistent or significant incapacity or substantial disruption of the ability to conduct normal life functions, or
- A congenital anomaly/birth defect.
- Important medical events that may not result in death, be life-threatening, or require hospitalizations may be considered serious when, based upon appropriate medical judgment they may jeopardize the patient or participant and may require medical or surgical intervention to prevent one of the outcomes listed in this definition. Examples of such medical events include allergic bronchospasm requiring intensive treatment in an emergency room or at home, blood dyscrasias or convulsions that do not result in inpatient hospitalization, or the development of drug dependency or drug abuse.

Serum dmLT-specific Ig response is defined as a  $\geq 4$ -fold rise in dmLT-specific serum

Ig titers over baseline.

ASC dmLT-specific Ig response is defined as  $\geq 8$  dmLT-specific Ig ASC / $10^6$  PBMC.

Serum dmLT-specific toxin neutralization response is defined as a  $\geq 4$ -fold rise over baseline in toxin neutralization titers.

ALS response is defined as a  $\geq 2$ -fold rise in ALS anti-dmLT-specific Ig titers over baseline.

Salivary response is defined as a  $\geq 4$ -fold rise over baseline in dmLT-specific salivary IgA titers.

Fecal response is defined as a  $\geq 4$ -fold rise over baseline in dmLT-specific fecal IgA titers.

ASC Homing response is defined as the presence of dmLT-specific circulating ASC expressing gut homing receptors (integrin  $\alpha 4\beta 7$  in the absence or presence of CD62L).

B memory response is defined as a  $\geq 0.05\%$  increase from baseline in the percentage of antigen-specific Ig /total Ig B memory cells.

T cell response is defined as an increase of  $>0.05\%$  from baseline cell percentage.

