#### dmLT-specific IgA ASC by ELISpot

The number and percentage of participants showing with  $\geq 8$  dmLT-specific IgA ASC /  $10^6$  PBMC as measured by ELISpot will be presented with exact (Clopper-Pearson) two-sided 95% CI by treatment arm at Days 1, 8, 15, 22, 29, 36, and any time for Oral and Sublingual Cohorts and at Days 1, 8, 22, 29, 43, 50, and any time for Intradermal Cohorts (Table 49 and Table 50).

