#### dmLT-specific IgG ASC by ELISpot

The number and percentage of participants showing with  $\geq 8$  dmLT-specific IgG ASC /  $10^6$  PBMC as measured by ELISpot will be presented with exact (Clopper-Pearson) two-sided 95% CI by treatment arm at

Days 1, 8, 15, 22, 29, 36, and any time for Oral and Sublingual Cohorts and at Days 1, 8, 22, 29, 43, 50, and any time for Intradermal Cohorts ([Table 51](#) and [Table 52](#)).

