**Table 50: ASC IgA Response Results by Time Point and Treatment Group, Oral & Sublingual Cohorts, Per Protocol Population**

**Table 51: ASC IgG Response Results by Time Point and Treatment Group, mITT Population**

Time Point	Statistic	Cohort A: Oral 5 µg dmLT (N=X)	Cohort B: Oral 25 µg dmLT (N=X)	All Oral Cohorts: Placebo (N=X)	Cohort C: Sublingual 5 µg dmLT (N=X)	Cohort D: Sublingual 25 µg dmLT (N=X)	All Sublingual Cohorts: Placebo (N=X)	Cohort E: Intradermal 0.3 µg dmLT (N=X)	Cohort E: Intradermal Placebo (N=X)
Pre-Dose 1a	n	x	x	x	x	x	x	x	x
	Proportion with ASC Response g	x.xx	x.xx	x.xx	x.xx	x.xx	x.xx	x.xx	x.xx
	95% CI	x.xx, x.xx	x.xx, x.xx	x.xx, x.xx	x.xx, x.xx	x.xx, x.xx	x.xx, x.xx	x.xx, x.xx	x.xx, x.xx
Post-Dose 1 Day 7b	n								
	Proportion with ASC Response g								
	95% CI								
Pre-Dose 2c	n								
	Proportion with ASC Response g								
	95% CI								
Post-Dose 2 Day 7d	n								
	Proportion with ASC Response g								
	95% CI								
Pre-Dose 3e	n								
	Proportion with ASC Response g								
	95% CI								
Post-Dose 3 Day 7f	n								
	Proportion with ASC Response g								
	95% CI								
Any Time Post Dose 1	n								
	Proportion with ASC Response g								
	95% CI								

Time Point	Statistic	Cohort A: Oral 5 µg dmLT (N=X)	Cohort B: Oral 25 µg dmLT (N=X)	All Oral Cohorts: Placebo (N=X)	Cohort C: Sublingual 5 µg dmLT (N=X)	Cohort D: Sublingual 25 µg dmLT (N=X)	All Sublingual Cohorts: Placebo (N=X)	Cohort E: Intradermal 0.3 µg dmLT (N=X)	Cohort E: Intradermal Placebo (N=X)
------------	-----------	---	--	--	---	--	--	--	--

N=Number of subjects in the mITT Population

a Day 1b Day 8c Day 15 for Oral & Sublingual Cohorts; Day 22 for Intradermal Cohortd Day 22 for Oral & Sublingual Cohorts; Day 29 for Intradermal Cohorte Day 29 for Oral & Sublingual Cohorts; Day 43 for Intradermal Cohortf Day 36 for Oral & Sublingual Cohorts; Day 50 for Intradermal Cohortg Defined as  $\geq 8$  IgA ASC/ $10^6$  PBMCs

Tables with similar format:

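### As worded, the secondary ASC endpoint is one either-isotype proportion, but the SAP plans only separate IgA and IgG proportions, so no planned table gives its rate or confidence interval

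*SAP*

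**What the plan says.** **The endpoint.** Protocol 3.2.2 words it as "dmLT-specific IgA or IgG ASC / 10^6 PBMC as measured by ELISpot", as a proportion of participants at any time after vaccination, with a threshold of more than 8. The Protocol Summary says the same. SAP 3.2.2 keeps the *or* ("dmLT-specific IgA or IgG ASC") but sets the threshold at 8 or more. In the same SAP list the serum endpoint is joined by *and*: "dmLT-specific serum IgG and IgA titers over baseline measured by Enzyme-Linked Immunosorbent Assay (ELISA". The ALS endpoint also uses *and*. The fecal and salivary endpoints concern IgA only.

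**The derivation.** SAP 3.3 has one generic entry, "ASC dmLT-specific Ig response is defined as" at least 8 per 10^6 PBMC, with no isotype named and no either-isotype variable.

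**The analysis.** SAP 8.2 has one paragraph for IgA (Tables 49 and 50) and another, headed "dmLT-specific IgG ASC by ELISpot", for IgG (Tables 51 and 52). Each gives a number, a percentage and an exact 95% interval for that isotype alone. The IgA paragraph lists "Days 1, 8, 15, 22, 29, 36, and any time for Oral and Sublingual Cohorts", so the pre-dose visit is among the listed days. The IgG paragraph is worded the same way, but the last row of the Table 51 shell is limited to the period after dose 1, while that of Table 49 is not.

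**The footnote.** Table 51 is titled "ASC IgG Response Results by Time Point and Treatment Group, mITT Population". Its footnote g defines response as at least 8 "IgA ASC/ $10^6$ PBMCs". Table 52 follows the Table 51 format and inherits the footnote.

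**The concern.** A named secondary endpoint should lead to a derived variable, an estimate and an interval. Here the endpoint text describes a participant who responds in either isotype, and the outputs describe each isotype on its own. An either-isotype rate depends on how far the two groups of responders overlap, which two separate tables do not show. Someone following the SAP as written would complete every planned ASC table and still lack a result for the endpoint as worded. Whether to combine the isotypes, and at which visits, would then be decided after the data are seen.

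The any-time row adds to this. The ASC threshold is an absolute count, not a rise over baseline. A participant already at the threshold on Day 1 could be counted as a responder in Table 49, although the endpoint concerns the period after vaccination.

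**Working it through.** No sample size, power or error rate in the documents depends on this endpoint, so there is no plan figure to reproduce. The check is whether the planned outputs can yield the endpoint.

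**1. Trace the endpoint through the SAP.**

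| Place | What it gives |
|---|---|
| Protocol 3.2.2, SAP 3.2.2 | One proportion, IgA or IgG, any time after vaccination |
| SAP 3.3 | Generic Ig response, no combined variable |
| SAP 8.2, Tables 49 and 50 | IgA proportion |
| SAP 8.2, Tables 51 and 52 | IgG proportion |
| Listing 9 | Both counts per participant and visit; no responder status, rate or interval |
| SAP Section 15 | No change to this endpoint recorded |

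The lists of tables and figures contain no combined ASC output.

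**2. Can the isotype rates supply the endpoint?** Let A be the number of IgA responders, G the number of IgG responders, n the group size and U the number responding in either isotype. Then

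max(A, G) ≤ U ≤ min(n, A + G).

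The lower limit is complete overlap and the upper limit the least possible overlap. SAP 4.4.3 gives n = 12 vaccinees per cohort, and Table 1 a minimum of 10 evaluable. A and G are assumptions, because the documents give no ASC response rates.

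| n | A | G | U, lowest | U, highest |
|---|---|---|---|---|
| 12 | 6 | 6 | 6/12 = 50% | 12/12 = 100% |
| 12 | 6 | 5 | 6/12 = 50% | 11/12 = 92% |
| 12 | 6 | 4 | 6/12 = 50% | 10/12 = 83% |
| 12 | 3 | 3 | 3/12 = 25% | 6/12 = 50% |
| 10 | 3 | 3 | 3/10 = 30% | 6/10 = 60% |

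The exact (Clopper-Pearson) 95% intervals are undetermined in the same way. With 12 vaccinees they are 5.5% to 57.2% for 3/12, 21.1% to 78.9% for 6/12, 51.6% to 97.9% for 10/12 and 73.5% to 100% for 12/12. As a check on the interval routine, 0 of 10 gives an upper bound of 30.85%, against 30.8% in SAP Section 5.

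**3. The Table 51 footnote.** Take a hypothetical participant with 0 IgA and 40 IgG ASC at Day 8. The endpoint and the IgG paragraph of SAP 8.2 both count this person as a responder. Table 49 does not, because it concerns IgA. Read literally, footnote g of Table 51 does not either. The footnote therefore contradicts the table's own title and SAP 8.2.

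**4. The threshold.** A count of exactly 8 is a response under the SAP (≥8) but not under the protocol (>8). SAP Section 15 does not mention the difference.

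**The case against.** The strongest reply is that *or* was never meant as a union. The objective in Protocol 3.1 and SAP 3.1 is to evaluate the IgG and IgA ASC response. SAP 3.3 uses the same generic Ig for serum and ALS, which are then reported by isotype, and SAP 8.2 places the two ASC proportions under secondary analyses. The documents are also not strict with conjunctions: read literally, *and* in the serum endpoint would require a joint responder, and none is computed. On this reading the endpoint is reported, once per isotype.

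That reading is possible, and it limits the claim. It does not remove the mismatch. The *or* appears in all three statements of this endpoint, while serum and ALS in the same list use *and*. The contrast rests on those two endpoints only, since fecal and salivary are IgA alone. If isotype-specific rates were intended, the endpoint text is what needs correcting.

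Two stronger inferences should be resisted. A reader might conclude that the endpoint is lost. It is not: Listing 9 prints both counts side by side, so the rate can be derived, and what is missing is a planned derivation and summary. A reader might also conclude that the IgG table will duplicate the IgA results. That would require a programmer to follow the footnote against both the Table 51 title and SAP 8.2. It looks like a copying slip, and it is not the reason the combined rate is absent.

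**Conclusion.** The point holds as a mismatch between endpoint and analysis. On the plain reading of the wording, no planned table gives the either-isotype ASC rate or its interval, and the planned isotype rates cannot determine it. In the illustrations with 12 vaccinees, the undetermined range is 25 to 50 percentage points wide (25% to 50% at its narrowest, 50% to 100% at its widest). Those widths rest on assumed counts and are not predictions. On the other reading, the endpoint is computed by isotype and the wording is wrong. A correction is needed in either case.

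The consequence is limited. The endpoint is secondary and descriptive, no hypothesis is tested, no primary endpoint is affected, and the data needed are already in the plan. The footnote, the threshold difference and the unrestricted any-time row are separate small defects on the same endpoint, to be settled at the same time.

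**What to change.** Choose one of two routes before the final analysis.

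1. **Keep the endpoint as worded.** Define in SAP 3.3 an either-isotype ASC responder: IgA or IgG ASC meeting the threshold at any visit after dose 1, with Day 1 excluded and each participant counted once. Report the number, percentage and exact 95% interval by treatment group, once for the mITT and once for the PP population, rather than repeating the row in both isotype tables. Keep the isotype rows as components.
2. **Reword the endpoint.** State isotype-specific proportions in both documents, and record the change in SAP Section 15.

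Under either route:

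- Reconcile the threshold between >8 (protocol) and ≥8 (SAP).
- Limit the last row of Tables 49 and 50 to the period after dose 1, as in Table 51, and bring the SAP 8.2 text into line.
- Correct footnote g of Table 51, and hence Table 52, to IgG.

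The first route costs one derived variable and one row per population; the second costs a wording change. Neither needs new data.

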### 3.2.3. Exploratory Outcome Measures

The **Exploratory Endpoints** to be used to evaluate the immune response to vaccination consist of the following:

- Geometric mean titers of dmLT-specific IgG and IgA in ALS measured by ELISA
- Geometric mean titers of dmLT-specific serum IgG and IgA measured by ELISA
- Mean and median number of dmLT-specific IgG and IgA ASC measured by EliSpot
- Geometric mean titers of dmLT-specific fecal IgA measured by ELISA
- Geometric mean titers of dmLT-specific salivary IgA measured by ELISA
- The proportion of participants with dmLT-specific memory B cell response as measured by ELISpot
- At any time after vaccination, the proportion of participants with anti-dmLT IgG and IgA ASC in circulation expressing gut homing receptors (integrin  $\alpha 4\beta 7$  in the absence or presence of CD62L) measured by EliSpot assay
- At any time after vaccination, proportion of participants with  $\geq 4$ -fold rise over baseline in toxin neutralization titers measured by Y-1 cell assay
- At any time after vaccination, the proportion of participants with dmLT-specific effector and memory T cell responses as measured by Cytometry by Time-of-Flight, or Mass Cytometry (CyTOF).

### 3.3. Study Definitions and Derived Variables

The baseline value will be defined as the last value obtained prior to the first vaccination/dose of study product. If a participant has repeated laboratory values on the same day, the value from the last evaluation will be used for analysis. Post-baseline, in the case of multiple observations (for example, from supplemental visits), the assessment value that is closest to the scheduled visit window will be used in the analyses. All the recorded data will be listed. If observations have the same distance to the scheduled assessment, the latest one will be used.

An adverse event (AE) is defined as any unfavorable and unintended sign (including an abnormal laboratory finding), symptom, or disease temporally associated with the use of a medicinal (investigational) product. Any medical condition that is present at the time that the participant is screened will be considered as baseline and not reported as an AE. However, if the severity of any pre-existing medical condition increases, it will be reported as an AE.

AEs are graded for severity and assessed for relationship to study product as defined below.

The severity of Laboratory, Vital Sign, and Solicited AEs are to be graded according to the standard criteria shown in [Table 7](#), [Table 8](#), and [Table 9](#). For all other AEs severity is defined as follows:

- Mild (Grade 1): Events require minimal or no treatment and do not interfere with the participant's daily activities.
- Moderate (Grade 2): Events result in a low level of inconvenience or concern with therapeutic measures. Moderate events may cause some interference with functioning and daily activities.
- Severe (Grade 3): Events interrupt the participant's usual daily activities and may require systemic drug therapy or other treatment. Severe events are usually incapacitating.

For all AEs relationship to study product is defined as follow:

- Related – There is a reasonable possibility that the study product caused the adverse event. Reasonable possibility means that there is evidence to suggest a causal relationship between the study product and the adverse event.
- Not Related – There is not a reasonable possibility that the administration of the study product caused the event.

A SAE will be defined as an adverse event or suspected adverse reaction that, in the view of either the site principal investigator or sponsor, results in any of the following outcomes:

- Death,
- A life-threatening adverse event, defined as an adverse event the occurrence of which, in the view of either the site principal investigator or sponsor, places the participant at immediate risk of death. It does not include an adverse event that, had it occurred in a more severe form, might have caused death.
- Inpatient hospitalization (defined by local practice as the study participant being present in the hospital greater than 24 hours) or prolongation of existing hospitalization,
- A persistent or significant incapacity or substantial disruption of the ability to conduct normal life functions, or
- A congenital anomaly/birth defect.
- Important medical events that may not result in death, be life-threatening, or require hospitalizations may be considered serious when, based upon appropriate medical judgment they may jeopardize the patient or participant and may require medical or surgical intervention to prevent one of the outcomes listed in this definition. Examples of such medical events include allergic bronchospasm requiring intensive treatment in an emergency room or at home, blood dyscrasias or convulsions that do not result in inpatient hospitalization, or the development of drug dependency or drug abuse.

Serum dmLT-specific Ig response is defined as a  $\geq 4$ -fold rise in dmLT-specific serum

Ig titers over baseline.

ASC dmLT-specific Ig response is defined as  $\geq 8$  dmLT-specific Ig ASC / $10^6$  PBMC.

Serum dmLT-specific toxin neutralization response is defined as a  $\geq 4$ -fold rise over baseline in toxin neutralization titers.

ALS response is defined as a  $\geq 2$ -fold rise in ALS anti-dmLT-specific Ig titers over baseline.

Salivary response is defined as a  $\geq 4$ -fold rise over baseline in dmLT-specific salivary IgA titers.

Fecal response is defined as a  $\geq 4$ -fold rise over baseline in dmLT-specific fecal IgA titers.

ASC Homing response is defined as the presence of dmLT-specific circulating ASC expressing gut homing receptors (integrin  $\alpha 4\beta 7$  in the absence or presence of CD62L).

B memory response is defined as a  $\geq 0.05\%$  increase from baseline in the percentage of antigen-specific Ig /total Ig B memory cells.

T cell response is defined as an increase of  $>0.05\%$  from baseline cell percentage.

